1.1 Background

Pulmonary arterial hypertension (PAH) is a progressive disease characterized by chronic elevation of mean pulmonary artery pressure (mPAP) and pulmonary vascular resistance (PVR), defined as a mPAP ≥ 25 mmHg at rest, a PVR > 240 dyn.s.cm⁻⁵, and pulmonary capillary wedge pressure (PCWP) < 15 mmHg (Galie et al 2015). The Updated Clinical Classification of Pulmonary Hypertension (Simonneau et al 2013) classifies pulmonary hypertension (PH) into five groups, based on similarities in clinical presentation, pathophysiology, prognosis and therapeutic approach. Within this classification, PAH is classified as Group 1 PH. Most cases of Group 1 PAH are idiopathic (i.e., not associated with known risk factors or conditions), but PAH also occurs in a heritable form and in association with other disorders, including collagen vascular diseases, congenital systemic-to-pulmonary shunts, ingestion of drugs/toxins or other systemic conditions such as HIV infection or portal hypertension.

A variety of arterial abnormalities characterize the pathology of PAH, including intimal hyperplasia, medial hypertrophy, adventitial proliferation, thrombosis in situ, varying degrees of inflammation, and plexiform arteriopathy. These remodeling changes are paramount in the pathogenesis of PAH, resulting in loss of luminal cross-section and increased PVR (Schermuly et al 2011), with only $< 20\%$ of PAH patients demonstrating a dynamic vasoconstrictive component of their disease (McLaughlin et al 2009). Progressive vascular remodeling and increased PVR results in increased workload for the right ventricle and right ventricular failure, which is the major cause of PAH associated mortality.

Over the last 20 years, significant advances have occurred in the treatment of PAH with the development of marketed therapies targeting three pathways: the endothelin, nitric oxide and prostacyclin pathways. Therapies targeting the prostacyclin pathway include the synthetic prostacyclin epoprostenol, prostacyclin analogs such as iloprost and treprostinil, and the IPR agonist selexipag. Prostacyclins are available via intravenous (epoprostenol, treprostinil), subcutaneous (treprostinil), inhaled (nebulized treprostinil and iloprost) and oral routes (treprostinil, beraprost (Japan only), selexipag). Despite these therapies, however, PAH remains a fatal disease with a median survival from diagnosis of 7 years (Benza et al 2012).

Prostacyclin (Prostaglandin I₂, PGI₂) is primarily produced by endothelial cells, formed from arachidonic acid via the cyclooxygenase pathway. The prostacyclin receptor (IPR) is widely expressed on multiple cell types, including vascular smooth muscle, fibroblasts, endothelium and various inflammatory cells (Woodward et al 2011). The vasodilatory action of prostacyclins is well validated in the clinic, and there is also growing non-clinical evidence that prostacyclins will impact upon the underlying structural changes that lead to increased vascular resistance, reversing the remodeling of pulmonary vessels. Inhaled iloprost has been shown to reverse vascular remodeling in a monocrotaline (MCT) induced PAH model in the rat (Schermuly et al 2005). In addition to normalization of PVR, iloprost reduced right heart hypertrophy and pulmonary vascular thickening. In another study using the MCT model, selexipag was also able to prevent vascular remodeling (Kuwano et al 2008).

Prostacyclins have also been associated with anti-inflammatory ([Hayashi et al 2010](#)) and anti-fibrotic effects ([Zhu et al 2010](#)).

Prostacyclins (e.g. epoprostenol, treprostinil, iloprost, selexipag) have been associated with improvements in pulmonary hemodynamics in PAH patients both acutely and following short term chronic dosing (e.g., 12-17 weeks) ([Barst et al 1996](#); [McLaughlin et al 2010](#); [Simonneau et al 2002](#); [Simonneau et al 2012](#)). These chronic effects are associated with improvement in exercise capacity (e.g., 6MWD) and functional status. In a 12 week open randomized study, epoprostenol was associated with improved survival in naive, severe Functional Class III/IV patients ([Barst et al 1996](#)). Most recently, in a time to clinical worsening (Phase 3 study with 1156 PAH patients treated for up to 4.2 years, selexipag decreased the risk of a worsening event versus placebo by 39%. Currently the effect of prostacyclins (and other PAH therapies) on chronic pulmonary vascular remodeling in the clinic is poorly characterized, in part due to the lack of validated endpoints/biomarkers to represent this process.

All prostacyclins have limitations impacting their safety and potential efficacy profile. Parenteral and oral IPR agonists are associated with on-target dose-limiting adverse events, including headache, jaw pain, nausea, diarrhea and hypotension, and require titration to an individual maximum tolerable dose. Nebulized iloprost and treprostinil are also dose limited by systemic adverse effects and have a relatively short duration of action, with both factors likely contributing to modest efficacy of these agents. As a result of these shortcomings, the initiation of prostacyclin therapy is delayed in some PAH patients, with a clear subsequent negative effect on prognosis ([Badagliacca et al 2012](#)).

To address these shortcomings, QCC374 has been designed as a chemically stable, selective inhaled IPR agonist for dry powder inhalation, with long duration of action (via optimized cell membrane affinity) and low systemic exposure (high plasma protein binding, rapid clearance). These characteristics are expected to lead to a considerably improved safety and tolerability profile and potentially increased efficacy compared to other members of the prostacyclin class.

1.2 Nonclinical data

Corporate Confidential Information

Corporate Confidential Information

Corporate Confidential Information

1.3 Clinical data

The safety, tolerability and pharmacokinetics of QCC374 was evaluated in healthy subjects in the QCC374X2101 study: Part 1 was a single ascending dose (SAD) study; Part 2 was a multiple ascending dose (MAD) study; and Part 3 was a within subject up-titration study in two cohorts. **Corporate Confidential Information**

Corporate Confidential Information

Corporate Confidential Information

Corporate Confidential Information

Corporate Confidential Information

1.3.3 Human pharmacodynamic data

There is no human pharmacodynamic data available.

1.4 Study purpose

The purpose of this study, as a long-term open-label safety extension to the Phase 2a study of inhaled QCC374 in adult patients with PAH, is to provide patients with the option to continue receiving QCC374 after completion of the QCC374X2201 trial, and monitor the long-term safety, tolerability and efficacy of QCC374 in patients with PAH.

2 Study objectives and endpoints

2.1 Primary objective(s)

Primary objective(s)	Endpoints related to primary objective(s)

To evaluate the safety and tolerability of QCC374 in patients with PAH over a two year period	
Adverse Events, Serious Adverse Events and all safety assessments

2.2 Secondary objective(s)

Secondary objective(s)	Endpoints related to secondary objective(s)

To assess the treatment effect of QCC374 in PAH patients not previously dosed with QCC374 (Arm 2: those subjects previously in the placebo group of QCC374X2201)	
6MWDKey RV function endpoints with echocardiography will include but not limited to tricuspid annular peak systolic velocity (TA S'), RV Tei index and RV fractional area change.

To evaluate the pharmacokinetics of QCC374 and its metabolite QCM441 in PAH patients not previously dosed with QCC374 (Arm 2: subjects previously in the placebo group of QCC374X2201)	
PK parameters (C_{max}, AUC_{last}, AUC_{tau}, C_{trough}) of QCC374 and QCM441 in plasma

3 Investigational plan

[figure not shown]
3.1 Study design

This is a multicenter, open label trial to assess the safety, tolerability, pharmacokinetics and efficacy of inhaled QCC374 over a two year period, in subjects with PAH who have completed study QCC374X2201. This study will have two arms (Figure 3-1). In Arm 1, subjects randomized to active in the QCC374X2201 study will continue on QCC374 at their highest stable dose. In Arm 2, the subjects randomized to placebo in the QCC374X2201 study will complete a titration scheme similar to that of the active arm in QCC374X2201 protocol. For subjects in both Arms, the assessments obtained during the Day 111 visit for the companion QCC374X2201 study (including physical examination, vital signs, pulse oximetry, ECG, spirometry, 6MWD, **Corporate Confidential** and laboratory data) will be used as the baseline values for this study. **Information**

[figure not shown]
This study may be amended in the future to increase the treatment duration period, as additional data emerges for QCC374 in PAH.

Figure 3-1 QCC374X2201E1 Extension Study Design

Arm 1

Arm 2

3.1.1 Study Periods

3.1.1.1 Screening

Arm 1 (patients who received QCC374 in the companion QCC374X2201 study):

The screening period (Day-8 to Day-1, max 8 days, min 1 day) may begin no earlier than Day 111 of the companion QCC374X2201 study. Subjects may be unblinded to the main study treatment allocation and provide informed consent for this study only after all of the Day 111 assessments have been completed for the QCC374X2201 study. Day -1 in the screening period may occur no earlier than Day 112 in the companion QCC374X2201 study. The goal is for patients to continue to receive QCC374 without interruption between the QCC374X2201 study and the extension study; no more than one week (7 days) can elapse between the last dose of study drug administered in the QCC374X2201 study and the first dose of study drug administered in the QCC374X2201E study.

Arm 2 (patients who received placebo in the companion QCC374X2201 study):

The screening period (Day -8 to Day -1, max 8 days, min 1 day) may begin no earlier than Day 111 of the companion QCC374X2201 study. Subjects may be unblinded to the main study treatment allocation and provide informed consent for this study only *after* all of the Day 111 assessments have been completed for the QCC374X2201 study. Day -1 in the screening period may occur no earlier than Day 112 in the companion QCC374X2201 study. No more than one week (7 days) can elapse between the last dose of study drug administered in the QCC374X2201 study and the first dose of study drug administered in the QCC374X2201E study.

3.1.1.2 Treatment Period

Arm 1 (patients who received QCC374 in the companion QCC374X2201 study):

Arm 1 consists of a treatment period of 720 days. Subjects may be dispensed study drug for the extension study no earlier than Day -1. The first study drug administration for the QCC374X2201E extension study will occur on Day 1. The first study drug administration may occur at home if the patient was dispensed study drug on Day -1.

Subjects will continue to receive QCC374 at the same dose that was administered during the proof of concept study (0.06 mg bid or lower if their individual maximum tolerated dose (MTD) if their individual MTD was below 0.06 mg bid). At any point during the treatment period, if a subject is on 0.06 mg and the investigator believes, based on their medical judgement, that the dose should be reduced due to the severity of adverse events, the investigator may reduce the dose to 0.03 mg. The investigator may subsequently increase the dose back to the 0.06 mg dose if the investigator believes this is appropriate based on their medical judgement. A follow-up phone call should be scheduled 7 days after adjustment to review safety and tolerability of the dose adjustment.

Visits will occur every three months during the extension treatment period, but the subject may need to return for drug resupply on a monthly basis. The resupply plan is country and site specific, and the expectations for resupply should be reviewed with the subject prior to the first dispensing of study medication.

Arm 2 (patients who received placebo in the companion QCC374X2201 study):

Arm 2 consists of a treatment period of 720 days, which is further divided into a Titration Period (Day 1 to Day 14), a Stable Dose Period (Day 15 to Day 112), and an Extension Treatment Period (Day 113 to Day 720) (Figure 3-1). Subjects in Arm 2 will be dispensed study drug on Day 1, and the first study drug administration for the QCC374X2201 extension study will occur on Day 1. This study drug administration must occur in the clinic.

Arm 2 Titration Period:

The starting dose of QCC734 for subjects in Arm 2 is 0.03 mg bid.

- On Day 7 the investigator will assess the subject's clinical status, and reported adverse events. The subject's dose will be increased to 0.06 mg unless the investigator believes, based on their medical judgement, that the dose should not be increased due to the severity of typical pharmacological effects of IP-receptor agonists, such as headache, jaw pain, myalgia, flushing and nausea.
- On Day 14 the investigator will assess the subject's clinical status, and reported adverse events. If the subject is not receiving the maximum 0.06 mg bid dose, the dose level will be increased to 0.06 mg, unless the investigator believes, based on their medical judgement, that the dose should not be increased due to the severity of adverse events. If this dosing scenario occurs, the subject is allowed to continue in the trial, and will continue to receive 0.03 mg bid.
- Following the Day 14 visit no further up-titrations above the Day 14 dose are allowed. On Day 21, if the subject was up-titrated on Day 14, a follow-up phone call visit will occur to review safety and tolerability.

Arm 2 Stable Dose Period:

During the stable dose period (Day 15 to Day 112), subjects will continue to receive the QCC374 dose established during the Titration Period (0.06 mg or 0.03 mg). At any point during the stable dose period, if a subject is on 0.06 mg and the investigator believes, based on their medical judgement, that the dose should be reduced due to the severity of adverse events, the investigator may reduce the dose to 0.03 mg. The investigator may subsequently increase the dose back to the 0.06 mg dose if the investigator believes this is appropriate based on their medical judgement. A follow-up phone call should be scheduled 7 days after adjustment to review safety and tolerability of the dose adjustment. During the stable dose period the subject will return for safety assessments every 28 days.

Arm 2 Extension Period:

Once the stable dose period is complete (following Day 112), subjects will continue to receive the same dose of QCC374 throughout the extension treatment period. Visits will occur every three months during the extension treatment period, but the subject may need to return for drug resupply on a monthly basis. The resupply plan is country and site specific and the expectations should be reviewed with the subject prior to the first dispensing of study medication.

3.1.1.3 End of Study Visit

For both Arm 1 and Arm 2, an end of study visit will occur 30 days after the last treatment visit. If a patient stops study medication prematurely, at a minimum a safety evaluation must be completed, and an attempt should be made to complete all assessments indicated at the End of Study Visit.

3.2 Rationale of study design

This open-label safety extension study will offer continuous QCC374 therapy to PAH patients who have completed the study QCC374X2201, and will provide long-term safety, tolerability and efficacy data.

- **Open-label:** This is a long-term study designed to assess safety and all subjects will receive active treatment
- **Dose-titration design:** This applies only to subjects in Arm 2 (i.e. those who are initiating treatment with QCC374 at the beginning of the study). All current marketed prostacyclins have an up-titration dosing strategy to increase prostacyclin tolerability. With up-titration significantly higher prostacyclin doses can be tolerated as compared to single dose administration
- **Starting dose:** This applies only to subjects in Arm 2 (i.e. those who are initiating treatment with QCC374 at the beginning of the study). The starting dose in Arm 2 is 0.03 mg, which is the same as the starting dose in the QCC374X2201 study.
- **Eligibility:** All subjects who completed QCC374X2201 are eligible to enroll. At the time of enrollment the efficacy of QCC374 in PAH patients will be unknown, as efficacy data from QCC374X2201 will not yet be available. All subjects who completed QCC374X2201 are eligible to enroll in the extension study in order to avoid an interruption in prostacyclin therapy.
- **Endpoints:** The primary endpoint of this study is the number of participants with adverse events as a measure of safety and tolerability. In addition, there are secondary

Corporate Confidential Information

Together these assessments are anticipated to inform future, larger studies of QCC374 in PAH.

3.3 Rationale for dose/regimen, route of administration and duration of treatment

Corporate Confidential Information

There is no comparator in this open-labeled extension study.

3.4 Purpose and timing of interim analyses/design adaptations

Corporate Confidential Information

3.5 Risks and benefits

Preclinical studies suggest that QCC374 may be of benefit for patients with PAH. However, QCC374 has not been studied previously in PAH patients and as such, the benefit for subjects participating in the study is unknown.

Prostacyclins, including the synthetic prostacyclin epoprostenol, the prostacyclin analogs treprostinil and iloprost, and the IPR agonist selexipag, have been associated a number of unwanted effects, including hypotension, jaw pain, flushing, headaches, an increased risk of bleeding, and gastrointestinal symptoms (nausea, vomiting, abdominal cramps and diarrhea). In addition, inhaled prostacyclin analogs have been associated with an increased risk of bronchospasm. As an inhaled IPR agonist, the potential risks of QCC374 are informed by prostacyclin adverse effects and some of these adverse events (headache, jaw pain, flushing) were observed in the FIH study, as described below. However, due to the QCC374's mode of administration, its high plasma-protein-binding (99.9% in humans) and its fast clearance, the systemic exposure to free QCC374 is very low, which is expected to minimize unwanted effects at the anticipated clinical doses. Furthermore, the data gained from the safety pharmacology and repeated dose toxicity studies, as well as FIH study, suggest a favorable safety and tolerability profile for QCC374.

The risk to subjects in this trial will be minimized by adherence to the eligibility criteria, close clinical monitoring, data review prior to beginning Part 2 and study stopping rules.

There may be unknown risks of QCC374 which may be serious and unforeseen.

3.5.1 Hypotension

In contrast to currently marketed prostacyclin analogs, QCC374 exerts its hemodynamic effects (on pulmonary as well as systemic vasculature) only at considerably higher doses than its antiproliferative effects. Thus, in animal studies considerable reversal of pulmonary vasculature remodeling was achieved in the absence of systemic hypotension.

Corporate Confidential Information

To further minimize risk in the QCC374X220E1 study, any subjects enrolling in this extension study who are receiving QCC374 for the first time (Arm 2, QCC374X2201 placebo patients) will use the same starting dose as the current starting dose in QCC374X2201 study. In the event of symptomatic hypotension, subjects will be treated with standard of care.

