Physical examination		X			X			X			X			X	X
Pulse oximetry		X			X			X			X			X	X
Vital Signs		X			X			X			X			X	X
Pregnancy test		X ³			X ³			X ³			X ³			X ³	X ³
Body weight															X
Blood chemistry		X			X			X			X			X	X
Hematology		X			X			X			X			X	X
Urinalysis		X			X			X			X			X	X
Spirometry		X			X			X			X			X	X
ECG evaluation		X			X			X			X			X	X
6-Minute Walk Test		X			X			X			X			X	X
		X			X			X			X			X	
Corporate Confidential Information		X			X			X			X			X	
														X	
														X	
														X	
Echocardiogram															
Corporate Confidential Information								X							

Epoch	Extension-Treatment ^{8,9}															
Visit Name	Long Term Follow Up													EOS (30 days post last treatment visit)		
Visit Numbers ¹	419	420	421	422	423	424	425	426	427	428	429	430	431	432	433 ⁸	
Study Day(s)	330 ±5	360 ±5	390 ±5	420 ±5	450 ±5	480 ±5	510 ±5	540 ±5	570 ±5	600 ±5	630 ±5	660 ±5	690 ±5	720 ±5	750 ±5	
Time (post-dose)	-	-	-	-	-	-	-	-	-	-	-	-	-	-	-	
Drug dispensation	X	X	X	X	X	X	X	X	X	X	X	X	X	X		
Study drug administration	Study drug administration will be bid - refer to Section 3.1 and Site Operations Manual															
PK blood collection	See Table 8-3 below															
Concomitant medications	As required															
Adverse events	As required															
Serious adverse events	As required															
Comments	As required															
Study/epoch completion information															X	X

¹ Visit structure given for internal programming purpose only

² The earliest that informed consent can occur is Day 111 in the companion QCC374X2201 study, and informed consent can occur no later than 7 days after Day 111.

³ Urine Pregnancy Test (females only)

⁴ Spirometry assessment during screening is only required if the spirometry testing session for V111 in the QCC374X2201 study did not meet ATS criteria for acceptability and reproducibility.

⁵ Domiciling is optional. The subject should remain in the clinic until all assessments are complete.

⁶ Assessments to be completed immediately prior to first QCC374 administration.

⁷ Assessments to be repeated prior to dosing if more than 4 days have elapsed since the D111 QCC374X2201 assessments.

⁸ If a patient stops study medication prematurely, at a minimum, a safety evaluation must be completed. Then an attempt should be made to complete all assessments listed under Visit 433, with the investigator making the determination of what is safe and feasible to complete.

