8.6.3 Vital Signs

At multiple time points referenced in the Assessment Schedule (Section 8.1), Blood Pressure, Pulse and Body Temperature will need to be recorded.

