7.2 Descriptive analyses

Subject demographics and other baseline characteristics

All data for background and demographic variables will be listed by arm and subject. Baseline characteristics will be presented both at Core (QCC374X2201) and Extension study (QCC374X2201E1) baseline. The Extension baseline, is defined, as the Extension study screening visit where the respective measurements are available (as per the assessment schedule) and Day 112 of the Core study where they are not. Summary statistics will be provided by arm.

Relevant medical history, current medical conditions, results of laboratory screens, drug tests and any other relevant information will be listed by treatment group and subject.

Treatment

Data for study drug administration (rescue medication) and concomitant therapies will be listed by arm and subject.

Summary tables will be used to present the proportion of subjects who reached each QCC374 dose, the proportion of subjects who had their dose reduced due to an adverse event, and the proportion of subjects who completed 16 weeks of treatment by dose subject received most from Day 15 to Day 112. Summary statistics for the number of days at each dose will be provided.

Vital signs

All vital signs data will be listed by treatment, subject, and visit/time and if ranges are available abnormalities (and relevant orthostatic changes) will be flagged. Summary statistics will be provided by arm and visit/time.

ECG evaluations

All ECG data will be listed by treatment, subject and visit/time, abnormalities will be flagged. Summary statistics will be provided by arm and visit/time.

Clinical laboratory evaluations

All laboratory data will be listed by treatment, subject, and visit/time and if normal ranges are available abnormalities will be flagged. A separate listing is provided presenting all parameters in a subject with any abnormal values. Summary statistics will be provided by arm and visit/time.

Adverse events

All information obtained on adverse events will be displayed by arm and subject.

The number and percentage of subjects with adverse events will be tabulated by body system and preferred term with a breakdown by arm. A subject with multiple adverse events within a body system is only counted once towards the total of this body system and arm.

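### Arm 2 blood pressure is measured before and after the first QCC374 dose, but no within-subject change and no count of subjects with a measured fall is planned

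*Protocol*

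**What the plan says.** Motive. Protocol Section 3.5 says that prostacyclins "have been associated a number of unwanted effects, including hypotension". Section 3.5.1 gives hypotension its own subsection, argues that "QCC374 exerts its hemodynamic effects (on pulmonary as well as systemic vasculature) only at considerably higher doses than its antiproliferative effects", and refers specifically to Arm 2, whose patients take QCC374 for the first time in this study.

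Data. In Table 8-2 (Protocol Section 8.1) the Vital Signs row for Arm 2 Day 1 is marked at 0m and at two later times. By column position these are 15 min and 4 h, although the alignment is not fully certain in the extracted table. Footnote 6 defines 0m: "Assessments to be completed immediately prior to first QCC374 administration". Section 8.6.3 gives the content: "Blood Pressure, Pulse and Body Temperature will need to be recorded".

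Analysis. SAP Section 7.2 lists vital signs by subject and visit/time and adds: "if ranges are available abnormalities (and relevant orthostatic changes) will be flagged. Summary statistics will be provided by arm and visit/time". Protocol Section 11.4.4 has the same structure, by Core study treatment. SAP Section 7.3 adds boxplots over time.

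Baseline. Protocol Section 3.1 says that the Core Day 111 assessments ("including physical examination, vital signs, pulse oximetry, ECG, spirometry, 6MWD", among others) "will be used as the baseline values for this study". For baseline characteristics, SAP Section 7.2 uses the extension screening visit where a measurement exists and Core Day 112 otherwise. SAP Section 6.1.1 uses Core Day 112 for the pharmacodynamic variables. Neither document states a reference reading for the Day 1 post-dose vital signs.

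**The concern.** The effect of a first inhaled dose on blood pressure is a question about individuals: who fell, by how much, and how soon. The schedule answers it with a pre-dose and post-dose pair in each Arm 2 subject, but the analysis treats each time point as a separate cross-section. A short-lived fall in a few subjects of a small arm can then pass as a modest shift in the mean.

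The point belongs to the primary objective, because Protocol Section 2.1 counts all safety assessments among the primary endpoints. The SAP does specify change from baseline for spirometry, which the protocol uses to monitor bronchospasm, another named risk. Vital signs have no equivalent sentence. Adverse event tables do not fill the gap: under Protocol Section 9.1 an abnormal test result becomes an adverse event only if it causes signs or symptoms, is judged clinically significant, or needs therapy. The tables are by arm and preferred term, not by relation to the first dose.

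**Working it through.** The plan gives no figure to reproduce. Protocol Section 11.7 has no sample size calculation and Section 11.4.2 no inferential analysis. The check compares what is collected with what is reported.

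**1. Outputs against the question**

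| Question about Arm 2, Day 1 | Planned output that answers it |
|---|---|
| Mean shift from 0m to a post-dose time | Yes, as the difference of two time-point means if data are complete |
| Individual readings | Yes, in the listing |
| Flag for an abnormal value | Yes, if ranges are available; none is given |
| Mean and SD of within-subject change | No |
| Number and percentage with a measured fall | No |
| Number with hypotension reported as an adverse event | Yes, over the whole study, not tied to the first dose |

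**2. Why separate summaries are not enough**

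The mean change is the post-dose mean minus the pre-dose mean, so the summaries supply it. The variance of the change is s0² + s1² − 2·r·s0·s1. The summaries supply s0 and s1 but not the within-subject correlation r. With s0 = s1 = s:

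SD(change) = s × √(2(1 − r))

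Assumptions, none from the documents: s = 14 mmHg, mean fall 5 mmHg, normal changes, and 20 mmHg as an illustrative cut-off only. The share falling by at least 20 mmHg is P(Z ≥ (20 − 5)/SD(change)).

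| r | SD(change), mmHg | z | Share falling ≥ 20 mmHg | Expected among 15 |
|---|---|---|---|---|
| 0.5 | 14 × 1.000 = 14.0 | 1.07 | 14.2% | 2.1 |
| 0.7 | 14 × 0.775 = 10.8 | 1.38 | 8.3% | 1.2 |
| 0.9 | 14 × 0.447 = 6.3 | 2.40 | 0.8% | 0.1 |

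All three rows have the same mean and SD at each time point, so the planned summary table cannot tell them apart.

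**3. What a count would tell**

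The size of Arm 2 is not stated. The protocol synopsis expects about 30 Core completers over both arms, so I take n = 8 to 19 as an assumed range. If no subject meets the threshold, the one-sided 95% upper bound on the rate is 1 − 0.05^(1/n). At a true rate of 10%, the chance of seeing at least one is 1 − 0.9^n.

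| n | Upper bound after 0/n | Chance of at least one at 10% |
|---|---|---|
| 8 | 31% | 57% |
| 10 | 26% | 65% |
| 15 | 18% | 79% |
| 19 | 15% | 86% |

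A count is therefore informative but coarse.

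**4. Which reference reading**

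Protocol Section 3.1.1.1 allows Day −1 no earlier than Core Day 112, so Day 1 is at least 112 + 1 − 111 = 2 days after the Day 111 reading. Table 8-2 marks no vital signs at extension screening, so the SAP rule for baseline characteristics would lead to Core Day 112. None of these is the same-day pre-dose value, which is collected and has no stated role as a reference.

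**The case against.** The strongest reply is that little is hidden. Summaries are by visit and time, so the Day 1 mean shift is visible. Every reading is listed by subject, and boxplots are planned. In an arm this small, a reader can go through the Day 1 listing by eye. Investigators are told in Protocol Section 9.1 to look for values outside notable ranges and for significant changes, and reported hypotension is counted. The study is descriptive and uncontrolled, so a missing count biases no planned estimate. The table shells mentioned in SAP Section 2 are not public and may contain more.

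Most of this stands, and it limits the point to a missing summary. It does not remove it: reading a listing by eye applies no rule set in advance, and the SAP sections that should state such a rule are not redacted and do not.

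Stronger readings are tempting but not supported:

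- A reader might infer that post-dose blood pressure will be compared with Core Day 111. No change from any baseline is specified for vital signs, so day-to-day noise in such a change cannot be held against the plan.
- A reader might infer that hypotension is never counted. It is, when reported as an adverse event.
- A reader might infer that the orthostatic flag has no data behind it. Protocol Section 8.6 places assessment methods in the Site Operations Manual, which is not available, so this cannot be established.
- A reader might take the pharmacology statement in Section 3.5.1 as the defect. It is rationale; the gap lies between Table 8-2 and the analysis sections.

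**Conclusion.** The point holds in limited form and for Arm 2 only, since Arm 1 took its first QCC374 dose in the Core study. The paired Day 1 readings are collected, but no planned output summarises the within-subject change from 0m or the number of subjects with a measured fall. The documents do not support the inference that the plan conceals a first-dose effect, because the mean shift and the individual readings remain available.

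The size can be shown only under assumptions: identical time-point summaries are compatible with anything from about 1% to 14% of subjects falling by 20 mmHg or more. This rests on the assumed SD, mean fall and correlations, and on reading the two post-dose columns as 15 min and 4 h. It is a worthwhile, inexpensive improvement to the reporting of a named risk under the primary objective, not an error that invalidates an analysis.

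**What to change.** In SAP Section 7.2, under vital signs, add for Arm 2 Day 1:

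1. A summary of each subject's change in systolic pressure, diastolic pressure and pulse from the Day 1 0m reading to each scheduled post-dose time.
2. The number and percentage of subjects whose post-dose value or fall meets a threshold that the sponsor sets before the data are reviewed, with the number of subjects having both readings as the denominator.
3. A sentence making Day 1 0m the reference for these changes.

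Elsewhere, reconcile Core Day 111, Core Day 112 and the extension screening visit, so that one vital-sign baseline is stated in both documents.

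The cost is a few lines of SAP text and one table. No new visits, measurements or clinical rules are needed.
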